4.3.3.4 Sensitivity/Supplementary analysis

The following sensitivity and supplementary analyses that are planned for the primary efficacy endpoint will also be conducted for the secondary efficacy endpoints:

- Pattern mixture model
- Censoring after intercurrent events
- Per-protocol analysis
- Slope analysis
- Divergence effect analysis

4.3.4 Tertiary Endpoints for Efficacy and Quality of Life

The baseline value and the change from baseline at each post-baseline visit for NPI-10 will be summarized by treatment group. An MMRM model will be used to analyze the change from baseline in NPI-10 using fixed effects of treatment group, time (categorical), treatment group-by-time interaction, baseline NPI-10, baseline NPI-10 by time interaction, baseline MMSE, AD symptomatic medication use at baseline (yes/no), region, and laboratory ApoE ϵ 4 status (carrier/non-carrier). Same methods as in the primary analysis will be considered for the covariance structure and the degrees of freedom.

For the following tertiary endpoints for patient-reported outcomes and quality of life, subject self-reported EQ-5D index score (SR), informant-rated subject EQ-5D index score (IR-S), and mPDQ-20, the baseline value and the change from baseline at each post-baseline visit will be summarized by treatment group. Additional analyses for these endpoints will be provided in a separate document.

4.3.5 Subgroup Analysis

Subgroup analyses will be performed for the primary endpoint (CDR-SB) and secondary endpoints (MMSE, ADAS-Cog13, ADAS-ADL-MCI). The following pre-defined subgroups will be considered:

- Laboratory ApoE ϵ 4 status (carrier or non-carrier)
- Baseline clinical stage (MCI due to AD or mild AD) per the Investigator's assessment based on the National Institute on Aging-Alzheimer's Association (NIA-AA) criteria
- Use of AD symptomatic medication at baseline (yes or no)

- Baseline MMSE (MMSE \leq 26 or MMSE \geq 27)
- Region (US, Europe/Canada/Australia, Asia; see Section 4.2.1 for definition of region)
- Age category (\leq 64, 65-74, \geq 75)
- Gender (female or male)

A selective set of subgroup analyses will be performed for Amyloid PET data. Details will be defined in Sections 4.4.

4.4 Amyloid PET Analysis

4.4.1 Amyloid PET substudy

Every subject enrolled into the study must have a positive amyloid PET scan by visual read either at screening or obtained within 12 months of screening. Subjects enrolled into the amyloid PET substudy will have the quantitative standard uptake value ratio (SUVR) scores at screening and at each planned post-baseline visit. The amyloid PET substudy will include a subset of approximately 400 subjects in countries other than Japan where PET scans will be performed using ^{18}F -florbetapir ligand, and a small subset of subjects in Japan where either ^{18}F -florbetapir ligand or ^{18}F -flutemetamol ligand will be used. In the placebo-controlled period, amyloid PET assessments are scheduled at screening, Week 26, and Week 78.

4.4.2 Amyloid PET SUVR regions-of-interest and reference regions

Amyloid PET standardized uptake value ratio (SUVR) is a quantitative measure of cerebral amyloid plaque burden. The SUVR will be calculated for the following target brain regions-of-interest (ROIs): composite ROI, frontal cortex, parietal cortex, lateral temporal cortex, sensorimotor cortex, anterior cingulate cortex, posterior cingulate cortex, medial temporal cortex, occipital cortex, striatum, and statistical ROI normalized to reference region activity. Additionally, SUVR ROIs including pons and deep subcortical white matter which are believed to be least affected by amyloid pathology will also be evaluated. The composite ROI will comprise of major cortical regions part of the frontal, parietal, lateral temporal, sensorimotor, anterior, posterior cingulate and occipital cortices to serve as a summary measure of global cerebral amyloid burden. The statistical ROI is a region of interest consisting of the posterior cingulate cortex, precuneus and medial frontal cortex that has been demonstrated to yield optimal group separation between subjects with low and high amyloid burden across different reference regions. A negative change from baseline in composite ROI SUVR indicates a reduction in amyloid burden and a negative treatment difference (aducanumab minus placebo) favors aducanumab. The composite ROI will serve as the ROI of primary focus.

The following reference regions will be employed: cerebellum, cerebellum cropped, cerebellar white matter, cerebellar grey matter, deep subcortical white matter, pons, cerebellum + pons, cerebellar white matter + pons, deep subcortical white matter + cerebellum, deep subcortical white matter + pons and deep subcortical white matter + cerebellum + pons. Cerebellum will serve as the reference region of primary focus.

CONFIDENTIAL

The information contained herein may not be used, disclosed, or published without the written consent of Biogen MA Inc.

The composite ROI SUVR using cerebellum as the reference region will be used as the primary endpoint for amyloid PET analysis.

4.4.3 Amyloid PET analysis population

There are two amyloid PET analysis population: ¹⁸F-florbetapir amyloid PET analysis population and ¹⁸F-flutemetamol amyloid PET analysis population.

The following background characteristics tables will be generated for the ¹⁸F-florbetapir amyloid PET analysis population and will be presented by treatment group: number of subjects enrolled by region and country, demography, baseline disease characteristics, medical history. The content of these tables will be the same as those described in section 4.2 for the ITT population, with the addition of baseline amyloid PET SUVR values summarized for the baseline characteristics of AD.

4.4.4 By visit summary and MMRM model

The baseline and change from baseline amyloid PET SUVR values will be summarized by treatment groups (placebo, low dose and high dose) and by visit for each of the target ROIs using cerebellum as the reference region for each of the amyloid PET analysis populations. In addition, the baseline and change from baseline amyloid composite ROI values will be summarized by treatment groups by visit for each of the reference regions for each of the amyloid PET analysis populations.

For the ¹⁸F-florbetapir amyloid PET analysis population, an MMRM model will be used to analyze change from baseline SUVR for each target ROI with cerebellum as the reference region. Fixed effects of the model will include treatment groups (placebo, low dose and high dose), visit (Week 26 and Week 78), treatment group-by-visit interaction, baseline SUVR (continuous), baseline SUVR by visit interaction, baseline MMSE (continuous), laboratory ApoE ε4 status (carrier and non-carrier), and baseline age (continuous). Visit and treatment group will be treated as categorical variables in the model along with their interactions. An unstructured covariance matrix will be used to model the within-patient variance-covariance errors. If the unstructured covariance structure matrix results in a lack of convergence in any of the parameters, the heterogeneous Toeplitz covariance structure followed by the heterogeneous first-order autoregressive covariance structure will be used for all the parameters. The Kenward-Roger approximation will be used to estimate the denominator degrees of freedom. Adjusted means for each treatment group, pairwise adjusted differences with placebo, 95% confidence intervals for the differences and associated p-values will be presented at week 26 and week 78. The same MMRM model will also be used to analyze the change from baseline SUVR for the composite ROI with each of the reference regions. No multiple comparison adjustment will be used for amyloid PET analysis.

Subgroup analysis will be conducted on the ¹⁸F-florbetapir amyloid PET analysis population using the same MMRM model for composite ROI using cerebellum as reference region for the following stratification factors: laboratory ApoE status (carrier or non-carrier, and this model will not use ApoE status as a covariate), baseline clinical stage (MCI due to AD or mild AD) and baseline composite ROI SUVR value in quartiles.

Visit windows for by visit analysis

For amyloid PET by visit summaries and MMRM models, the analysis visit should be defined using visit windows (see Table 4 below). The rationale is to use the same analysis visit windows as for the efficacy endpoints for Week 26 and Week 78. If there is more than 1 value in the same analysis visit window (>1 value for the same analysis visit) for a certain parameter for a subject, then the closest record to the target visit day will be used for the by visit analysis. If they are with the same distance from the target visit day, then the record with the later time will be used for the by visit analysis.

Table 4: Visit Windows for amyloid PET data

Analysis visit	Target visit day	Analysis visit window
Baseline	1	Most recent non-missing pre-dose value
Week 26	183	[92, 266]
Week 78	547	[449, the end day of the placebo-controlled period**]

* The end day of the placebo-controlled period is the last day before the first infusion in LTE for subjects who enter in LTE, and is the last day in study for subjects who do not enter LTE.

4.4.5 Correlation between amyloid PET and CDR sum of boxes

Pearson and Spearman correlation

Pearson and Spearman correlations between change from baseline amyloid PET composite ROI using cerebellum as reference region at Week 78 and change from baseline CDR-SB at Week 78 will be conducted by treatment groups (placebo, low dose and high dose, and active total) in the ¹⁸F-florbetapir amyloid PET analysis population. Pearson and Spearman partial correlations adjusting for baseline amyloid PET composite ROI and baseline CDR-SB will also be conducted by treatment groups at Week 78. The estimated correlation coefficients, p-values and the 95% confidence intervals will be provided. Given that reductions in cerebral β -amyloid ($A\beta$) content may precede clinical effects (e.g., slowing of clinical decline), Pearson and Spearman correlations and partial correlations between change from baseline amyloid PET composite ROI at Week 26 and change from baseline CDR-SB at Week 78 will also be conducted.

Correlation analysis will be done on each individual study as well as in the pooled data of the 221AD301 and 221AD302 studies. The correlation analysis based on the pooled data will be considered as the primary analysis.

4.5 Safety Analysis

4.5.1 General Considerations

Analysis population

Safety population will be used for safety analyses of AEs, clinical laboratory data, Columbia Suicide Severity Rating Scale (C-SSRS) data, ECG data and vital sign data (all the safety data except for ARIA data). Safety MRI population will be used for analyses of ARIA data.

Safety treatment groups

Different from the randomization treatment groups, if a subject who was randomized to placebo group accidentally received one or more doses of the active treatment during the study, he/she will be classified as either low or high dose group for all the safety analyses, depending on the ApoE status and the maximal dose level of the active treatment received (Table 5). A listing of such subjects will be provided, as described in section 4.2.5. Safety treatment groups will be the same as the randomization treatment groups for other subjects (subjects randomized to active treatment groups, and subjects randomized to placebo without any accidental active dose). Safety treatment groups will be used for all the safety analyses unless otherwise specified.

Table 5: Safety treatment groups for placebo subjects with accidental active treatment

Randomization treatment group	Randomization ApoE status	Safety treatment group classification based on the maximum dose level of the accidental active treatment		
		>0 to 3 mg/kg	>3 to 6 mg/kg	>6 mg/kg
Placebo	ApoE ε4 (+)	Low dose	High dose	High dose
	ApoE ε4 (-)	Low dose	Low dose	High dose

Safety analysis displays

AEs, clinical laboratory data, C-SSRS data, ECG data and vital sign data (all the safety data except for ARIA data) will be summarized by treatment group (placebo, low dose, high dose and BIIB037 total; analysis display A in Appendix 6.1), unless otherwise specified. All the ARIA related tables will be presented by treatment group stratified by ApoE status (3 columns under each treatment group: ApoE ε4+, ApoE ε4- and total; analysis display B in Appendix 6.1), unless otherwise specified. A subset of AE tables will also be presented by treatment group stratified by ApoE status in addition to by treatment group. All the listings will be presented by treatment group stratified by ApoE status.

Incidence, incidence proportion and incidence rate

- Incidence and incidence proportion will be provided in incidence tables. Incidence is defined as the number of subjects who experienced an event. Incidence proportion is defined as the number of subjects who experienced an event divided by total number of subjects in the analysis population, i.e., percentage. Each subject will be counted only once within each category.

	Statistical Analysis Plan Placebo-Controlled Period	Final V1.0
---	---	-------------------

- Incidence and incidence rate will be provided in incidence rate tables. Two different kinds of incidence rate tables will be provided as appropriate for different analyses. Definitions are provided below.
 - (1) Follow-up adjusted incidence rate – defined as the number of subjects who experienced an event divided by the total of entire follow-up time among the subjects in the analysis population. The entire follow-up time for a subject is defined as the time from the first dose until the last day on study. Each subject will be counted only once within each category.
 - (2) Exposure-adjusted incidence rate (EAIR) – defined as the number of subjects who experience an event divided by the total exposure adjusted follow-up time among the subjects in the analysis population. The exposure adjusted follow-up time is defined as the time from the first dose until the initial occurrence of the event for those who experienced an event, or from the first dose until the end of follow-up (the last day on study) for those who did not. Each subject will be counted only once within each category.

4.5.2 Clinical Adverse Events

Treatment-emergent AEs (TEAEs)

All AEs will be analyzed based on the principle of treatment emergence. A treatment-emergent AE was defined as an AE that started or worsened after the start of first infusion of study treatment.

To define treatment emergence for AEs with missing start or stop date or time the following additional criteria will be used:

- if both the start and stop dates for a particular AE are missing, then that AE is considered treatment emergent;
- if the start date for a particular AE is missing and the stop date/time falls after the first dose date/time, then that AE is considered treatment emergent;
- if the start date for a particular AE was the same as the first dose date, and the start time was missing, then that event is considered treatment emergent.

For AEs with a partial start date, the year/month of the event date will be compared to that of the first dosing date to determine whether the event is treatment emergent.

In addition, SAEs that occurred since a subject was screened in the study and prior to the first infusion of study treatment, which by definition are not treatment-emergent, will be analyzed separately.

Only TEAEs will be included in the AE tables, unless otherwise specified. Listings of AEs will include all events, whether treatment-emergent or not.

As specified in the protocol, subjects were expected to return to the study site for an End of Study visit 18 weeks after the last administration of study treatment. However, some subjects may elect to continue study participation on a modified schedule after discontinuing treatment, possibly in substantial excess of 18 weeks. For most general AE summaries, AEs

CONFIDENTIAL

The information contained herein may not be used, disclosed, or published without the written consent of Biogen MA Inc.

with an onset more than 18 weeks after the last dose will be excluded (will specify in the footnote of the specific table). For incidence rate analyses excluding AEs more than 18 weeks after the last dose, the “last day on study” in follow-up time calculation will be replaced with “18 weeks after last dose or last day on study, whichever earlier”. Summaries of deaths and AEs leading to study withdrawal, and other selected analyses will include all AEs regardless of the time since the last dose. Listings will include all AEs, unless otherwise specified.

4.5.2.1 Summary and incidence analysis

Overall summary of AE table will summarize the number of subjects with any AE, with any AE by maximum severity, the number of subjects with any related AE (related to study drug as assessed by investigator), the number of subjects with SAE, the number of subjects with related SAE, the number of subjects with AE leading to study drug discontinuation, the number of subjects with AE leading to study withdrawal, and the number of deaths. This table will be done by treatment group as well as by treatment group stratified by ApoE status.

The sorting order for AE incidence tables, unless otherwise specified, will be by decreasing frequency order of “BIIB037 total” column within each category in the tables presented by treatment group, and by decreasing frequency order of “BIIB037 high dose total” column within each category in the tables presented by treatment group stratified by ApoE status. A subject is counted only once within each category in each table. For example, for the table of AEs by system organ class and preferred terms sorted by decreasing frequency presented by treatment group, system organ class will be presented in decreasing frequency order of BIIB037 total column, and within each system organ class, preferred terms will be presented in decreasing frequency order of BIIB037 total column. A subject is counted only once within each system organ class and preferred term.

The following AE incidence tables will be provided (presented both by treatment group and by treatment group stratified by ApoE status, unless otherwise specified):

1. AEs by system organ class and preferred term sorted by decreasing frequency
2. AEs by system organ class and preferred term sorted by alphabetical order (by treatment group)
3. AEs by system organ class, high level group term and preferred term (by treatment group only)
4. AEs by system organ class (by treatment group)
5. AEs with at least 2% higher in incidence for either low or high dose compared to placebo by system organ class and preferred term
6. AEs by preferred term
7. AEs with an incidence of 5% or more in any treatment group by preferred term
8. Severe AEs by system organ class and preferred term (by treatment group)
9. Severe AEs by preferred term
10. AEs by maximum severity by system organ class and preferred term (by treatment group) (System organ class will be presented alphabetically. Preferred terms will be presented in decreasing frequency order. Maximum severity will be presented within each preferred term in the order of mild, moderate, severe, unknown and total. A

CONFIDENTIAL

The information contained herein may not be used, disclosed, or published without the written consent of Biogen MA Inc.

subject will be counted only once at the maximum severity within each system organ class and preferred term.)

11. AEs by maximum severity by preferred term (by treatment group) (Preferred terms will be presented in decreasing frequency order. Maximum severity will be presented within each preferred term in the order of mild, moderate, severe, unknown and total. A subject will be counted only once at the maximum severity within each preferred term.)
12. Related AEs by system organ class and preferred term
13. SAEs by system organ class and preferred term
14. SAEs by preferred term
15. Related SAEs by system organ class and preferred term
16. AEs that led to discontinuation of study treatment by system organ class and preferred term
17. AEs that led to withdrawal from study by system organ class and preferred term
18. SAEs with fatal outcome by system organ class and preferred term
19. AEs that occurred within 2 hours from infusion start by system organ class and preferred term (by treatment group)
20. AEs by 12 weeks intervals from first infusion to the end of study by system organ class and preferred term (by treatment group)
21. Pre-treatment SAEs that occurred since screening and prior to first infusion by system organ class and preferred term

The following listings will be provided.

1. Listing of AEs
2. Listing of SAEs
3. Listing of AEs that led to discontinuation of study treatment
4. Listing of AEs that led to withdrawal from study
5. Listing of AEs that occurred within 2 hours from infusion start
6. Listing of AEs related to PET ligands
7. Listing of SAEs with fatal outcome
8. Listing of AEs for subjects with treatment-emergent positive anti-BIIB037 antibody

4.5.2.2 Incidence rate analysis

Follow-up adjusted incidence rate for the placebo-controlled period will be summarized by system organ class and preferred terms both by treatment group and by treatment group stratified by ApoE status.

4.5.2.3 Subgroup analysis for protocol version 4

Due to the change in maximal dose from 6 mg/kg to 10 mg/kg for ApoE ε4 carrier high dose group in protocol version 4, not all subjects have had opportunity to receive the protocol specified high dose (6 doses in titration before receive 10mg/kg) in the placebo-controlled period. Incidence tables of AEs and SAEs will be provided for ApoE ε4 carriers who were randomized to the high dose group, stratified by the expected number of doses at 10 mg/kg (categories of 0, 1-6, 7-13, 14, and a total column of having at least one dose) a subject would have received based on the first infusion date and the date consenting to protocol version 4. Randomization treatment groups will be used for this analysis.

4.5.3 ARIA – AE of special interest

4.5.3.1 Background

ARIA is an AE of special interest in this study. Please see protocol section 7.2.1 for ARIA management and dose disposition guidelines. Since ARIA is a brain MRI finding, ARIA data are collected under two data sources: (1) safety MRI data as recorded on brain MRI worksheet by central MRI reader; (2) AE eCRF. For each ARIA event, the information of start/end date, severity, locations in brain regions and status on MRI scan is collected on the brain MRI worksheet by central MRI reader. ARIA severity is determined by central MRI reader based on number and size of the ARIA regions on imaging. An AE record is then entered into the eCRF by the investigator with the start/end date and severity information from brain MRI worksheet, and with information on the symptomatic status and action taken towards study drug. If ARIA is symptomatic, the symptoms will be entered into AE eCRF and the severity of the symptoms will be determined by the investigator. AE eCRF data will be used as the primary source for ARIA analysis as it contains the complete information of ARIA as well as associated symptoms. Safety MRI data will also be used to show the consistency between two data sources, provide details on MRI assessments, and for any specific analysis that requires information from MRI.

ARIA includes ARIA-E (vasogenic edema) and ARIA-H (hemorrhage). ARIA-H includes ARIA-H microhemorrhage, ARIA-H macrohemorrhage and ARIA-H superficial siderosis. Table 6 shows the reported term on MRI worksheet, the corresponding reported term on AE eCRF, and the MedDRA preferred term and lower level term for each type of ARIA.

Table 6: Reported and MedDRA terms for ARIA

Reported term on MRI worksheet	Reported term on AE eCRF	MedDRA version 21.0 preferred term	MedDRA version 21.0 lower level term
ARIA-E	Asymptomatic ARIA-E Symptomatic ARIA-E	Amyloid related imaging abnormality-oedema/effusion	ARIA-E

CONFIDENTIAL

The information contained herein may not be used, disclosed, or published without the written consent of Biogen MA Inc.

ARIA-H microhemorrhage	Asymptomatic ARIA-H (Microhemorrhage) Symptomatic ARIA-H (Microhemorrhage)	Amyloid related imaging abnormality-microhaemorrhages and haemosiderin deposits	ARIA-H
ARIA-H macrohemorrhage	Asymptomatic ARIA-H (Macrohemorrhage) Symptomatic ARIA-H (Macrohemorrhage)	Amyloid related imaging abnormality-microhaemorrhages and haemosiderin deposits	ARIA-H
ARIA-H superficial siderosis	Asymptomatic ARIA-H (Superficial Siderosis) Symptomatic ARIA-H (Superficial Siderosis)	superficial siderosis of the central nervous system	superficial siderosis of the central nervous system

For any specific ARIA event, the start date of the duration based on MRI is the date of the MRI assessment that initially identifies the ARIA event, and the end date of the duration based on MRI is the date of the MRI assessment that shows the complete resolution of this ARIA event (in the case of ARIA-E), or the date of the MRI assessment that shows ARIA being stable (in the case of ARIA-H). Stable was defined as ‘No change’ or ‘decrease’ in number, size, severity or number of locations between 2 consecutive MRIs including the initial detection MRI and the follow-up MRIs.

For symptomatic ARIA events, if there is any related symptom that proceeds the first MRI identification, then the symptom onset date will be used as the start date of the symptomatic ARIA duration. The end date of the symptomatic ARIA duration will be the date of the resolution or stable MRI as defined above for the duration based on MRI.

If the severity increases, or the event changes from asymptomatic to symptomatic, or from non-serious to serious, more than one AE records will be added to eCRF to capture the change with new start/end AE dates (the end date of the previous record will be the start date of the next record). For analysis, records with changes in severity or symptomatic status or seriousness are considered as a single ARIA event. The severity/symptomatic status/seriousness for that event is defined as the worst level among all the AE records that belong to that event.

If the same type of ARIA event happens again after the previous event has ended, then it is considered a recurrent event of ARIA of that type. Recurrent events will be referred as the second event, the third event, and etc.

If the duration based on MRI of an ARIA-E event overlaps with the duration based on MRI of an ARIA-H event, then these 2 ARIA events are considered as concurrent events.

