Montreal Cognitive Assessment (MOCA) is performed at baseline and at each unscheduled ARIA monitoring visit for ARIA subjects (approximately every 4 weeks) except for mild asymptomatic microhemorrhage subjects. An incidence table of subjects with ARIA events whose MOCA total scores decrease 2 points or more from baseline will be provided. A listing of MRI assessments and MOCA total scores for subjects with ARIA events will be provided.

Line plots of MMSE mean change from baseline values and standard errors at each planned visit (baseline, Week 26, Week 50 and Week 78) will be provided by treatment group stratified by ApoE status and with stratification on the following factors:

- (1) ARIA-E severity based on MRI. The groups are: subjects without ARIA-E, subjects with mild ARIA-E, subjects with moderate ARIA-E and subjects with severe ARIA-E.

- (2) Within ARIA-E subjects, stratify by the severity of the concurrent symptoms based on AE eCRF. The groups are: subjects without symptoms, subjects with mild symptoms, subjects with moderate symptoms, and subjects with severe symptoms.

For subjects with recurrent ARIA-E events, the first ARIA-E event will be used for the classification for each of the factors.

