4.5.3.3 Summary of recurrent ARIA-E

Follow-up adjusted incidence rate of subjects with ARIA-E, with 2 or more events of ARIA-E, with 3 or more events of ARIA-E and with more than 3 events of ARIA-E based on their entire follow-up time will be summarized based on AE eCRF. The entire follow-up time is from the first dose until the last day in the placebo-controlled period.

Number of total ARIA-E events and the MRI severity of each event will be summarized based on AE eCRF. Number of total symptomatic ARIA-E events, the MRI severity of each symptomatic event and the severity of the symptoms of each symptomatic event will be summarized based on AE eCRF.

Summary of first ARIA-E events table based on AE eCRF will summarize the number of subjects with a first event of ARIA-E, the MRI severity of the events, the symptomatic status of the events, the severity of the symptoms for symptomatic events, whether SAE or not, number of resolved and unresolved events, duration of the resolved events, time from first infusion in study (active or placebo) to onset, number of doses received since the start of the study to onset, dose level of the last infusion received prior to onset, dosing status (continue as planned, dose interrupted, dose reduced, or dose discontinued) after the events, and the number of subjects with recurrent ARIA-E events. The same summary of first ARIA-E events table will also be done on subjects who had recurrent ARIA-E events.

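### ARIA enters the AE severity field with its MRI grade, so any-AE and system-organ-class severity totals combine imaging and clinical scales, and no planned table gives a severe-AE total on one clinical scale

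*SAP*

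**What the plan says.** Section 4.5.3.1 of the placebo-controlled SAP sets the source of ARIA severity: "ARIA severity is determined by central MRI reader based on number and size of the ARIA regions on imaging". That grade then goes into the AE form: "An AE record is then entered into the eCRF by the investigator with the start/end date and severity information from brain MRI worksheet". Symptoms are handled separately: "If ARIA is symptomatic, the symptoms will be entered into AE eCRF and the severity of the symptoms will be determined by the investigator". Table 6 in the same section lists both forms of each ARIA type as reported AE terms, for ARIA-E as "Asymptomatic ARIA-E Symptomatic ARIA-E", and maps both to one preferred term.

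Section 4.5.3.3 confirms that the AE form holds the imaging grade: "Number of total ARIA-E events and the MRI severity of each event will be summarized based on AE eCRF".

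Section 4.5.2 puts all treatment-emergent AEs into the AE tables unless something else is specified. Section 4.5.2.1 then asks for an overall summary that includes "the number of subjects with any AE, with any AE by maximum severity". It also lists severe-AE tables (items 8 and 9) and maximum-severity tables (items 10 and 11). None of these mentions ARIA.

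**The concern.** An imaging grade measures lesion burden, while an AE severity grade is normally read as how badly the patient was affected. If both sit in one field under the same words, a count of subjects with a severe AE no longer measures one thing. A subject with extensive ARIA on the scan and no symptoms is counted alongside subjects who were clinically severely ill.

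ARIA is the plan's AE of special interest, and section 2.1 provides for dose adjustment when it occurs, so the mixing probably falls mainly in the active arms. A difference between aducanumab and placebo in the any-AE severe total could then be imaging, clinical or both, and the total alone would not show which.

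**Working it through.** This is a check of the text. I traced the severity value from the scan to the general tables and looked for a rule that would stop or regrade ARIA on the way.

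1. **Source of the grade.** Section 4.5.3.1: the central reader grades by number and size of regions. No clinical input is named.
2. **Entry in the AE form.** Section 4.5.3.1 carries the worksheet severity into the AE record. Section 4.5.3.3 reads MRI severity back from the AE form, which fits only if the form holds it.
3. **Same labels.** The MMSE plots in section 4.5.3.2 group subjects by MRI grade as "subjects without ARIA-E, subjects with mild ARIA-E, subjects with moderate ARIA-E and subjects with severe ARIA-E". The maximum-severity tables use mild, moderate and severe too, so the value itself does not show which scale it is on.
4. **Asymptomatic ARIA is an AE.** Table 6 gives it a reported term and a MedDRA preferred term. Since the investigator grades symptoms only, an asymptomatic record carries the MRI grade and no clinical grade.
5. **Entry to the general tables.** Section 4.5.2 includes all treatment-emergent AEs by default. The overall summary and items 8 to 11 of section 4.5.2.1 state no exclusion, no substitute grade and no footnote.
6. **LTE plan.** Section 3.5.3.1 of the LTE SAP refers back to the placebo-controlled SAP for ARIA. Section 3.5.2.1 has the same overall summary with severe-AE and maximum-severity tables, and section 3.5.2.2 has severe-AE tables. Neither has an ARIA rule.

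Let C be the subjects with at least one clinically severe event and M the subjects with at least one ARIA event graded severe on MRI. Then

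- severe-AE subjects as recorded = C ∪ M;
- severe-AE subjects on the clinical scale = C;
- difference = subjects in M who are not in C.

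The last group includes asymptomatic MRI-severe ARIA, and also MRI-severe ARIA with only mild or moderate symptoms, unless the subject has another severe AE. ARIA graded mild or moderate on MRI adds nothing to the severe count; it enters the mild or moderate rows of the maximum-severity tables.

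The reverse case does not remove anyone. ARIA that is mild on MRI with severe symptoms shows as mild on its own row, but the severe symptom is entered in the AE form with the investigator's grade, so the subject remains in C.

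**Illustration only; neither input is in the documents.** Assume 10% of subjects in every arm have a clinically severe AE, and that 2%, 5% or 10% of the high-dose arm and nobody on placebo have asymptomatic MRI-severe ARIA. With no overlap between the groups, the high-dose total is 10 + 2 = 12%, 10 + 5 = 15% or 10 + 10 = 20%, against 10% on placebo. With complete overlap it stays at 10% in each case. The arithmetic shows the mechanism and is not an estimate.

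**The case against.** The best counter-argument is that the SAP discloses all of this. It says where ARIA severity comes from, and how an investigator fills in the form is normally a matter for the protocol or the form instructions. Section 4.5.1 also twice describes the general safety data as excluding ARIA data, which could mean that ARIA never reaches tables 8 to 11. That wording, however, governs which population is used and how columns are laid out. No table in section 4.5.2.1 is defined as leaving ARIA out. If exclusion was intended, the SAP needs to say so.

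Several limits do stand:

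- Items 8 to 11 are broken down by preferred term, and Table 6 gives each ARIA type an identifiable term, so a reader can see how many severe cases lie on those rows.
- Sections 4.5.3.2 and 4.5.3.3 report imaging severity, symptomatic status and symptom severity separately, with an incidence table and listing for subjects whose symptoms were severe. The clinical information is not lost.
- Section 4.5.3.1 treats seriousness as an attribute separate from severity, so the SAE tables are untouched.
- Section 1.3.2 names AEs, SAEs and MRI findings as safety endpoints. Severe AEs are not named there, and the SAP plans no test on them.

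A reader might infer that every asymptomatic scan finding counts as a severe AE. The text supports this only for ARIA that the central reader grades severe. A reader might also infer that a true excess of clinically severe events would be diluted. It would not, since clinically severe symptoms are still counted. Adding MRI-severe subjects mainly to the active arms would widen the difference from placebo.

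Finally, taking asymptomatic ARIA out of the only severe-AE total would be hard to defend. It would remove asymptomatic macrohemorrhage, a listed term in Table 6, and lower the count mainly in the active arms. The as-recorded tables should therefore stay.

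**Conclusion.** The point holds in a limited form and is a cheap improvement. The any-AE and system-organ-class severity totals in section 4.5.2.1 combine imaging-graded ARIA with clinically graded events, and asymptomatic ARIA graded severe on MRI counts as a severe AE. No planned table in either SAP gives a severe-AE total on one clinical scale. The preferred-term rows and the ARIA tables let a reader see the two scales, but cannot be combined into that total, because subjects may have both kinds of event.

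The size cannot be derived: the SAP gives neither ARIA rates nor a distribution of MRI grades. The conclusion rests on two readings: that the general tables include ARIA, since nothing excludes it, and that severity of other AEs is the investigator's clinical grade. The second is the usual meaning of the field, but the SAP states it only for ARIA symptoms. That the mixing falls mainly in the active arms is likely, not shown.

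**What to change.** In section 4.5.2.1, state that ARIA terms enter the overall AE summary and items 8 to 11. Keep these tables as recorded, with a footnote that the severity of ARIA terms is the central reader's MRI grade.

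Add a parallel version of the overall severity summary and of the severe-AE and maximum-severity totals. In it, each ARIA event counts at the investigator-rated severity of its symptoms, and asymptomatic ARIA appears on its own line by MRI grade. Leave the section 4.5.3 tables as they are. Make the same change for the severity tables in sections 3.5.2.1 and 3.5.2.2 of the LTE SAP.

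The cost is SAP wording, a footnote and one extra derivation. Symptom severity is already on the AE form, and section 4.5.3.2 already plans to report it. The drawback is a second set of severity totals, which the clinical study report must explain.
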